# Study Summary

Title	Kinetic Anesthesia Device for Lidocaine Injection: a randomized split-body study of the effects of kinetic anesthesia devices on pain of lidocaine injection in healthy volunteers.
Short Title	Kinetic Anesthesia Device Study
IRB Number	Pending
Protocol Number	Pending
Phase	Not applicable
Methodology	open label split-body crossover trial with randomization of subjects to one of three injection locations, and randomization of the order of injection with and without intervention.
Cturdu /	Recruitment and enrollment period: 2 months Subjects' length of participation in the study: 1 visit.
Duration	Project date of the proposed study: Recruitment and enrollment will commence with
	IRB approval. Total duration: 6 months in total for full data processing.
Study Center(s)	Single center – the study will take place at the Perelman Center For Advanced Medicine.
	Primary: To determine the effect of kinetic devices versus no device on pain of lidocaine injection as measured by 100mm visual analog scale.
Objectives	Secondary: To determine if the effect of kinetic devices on pain of local anesthetic injection is associated with anatomic location of the injection
	To determine patient preference of kinetic device versus no device for local anesthetic injection
	To gather qualitative data on changes to the patients experience of pain and overall experience using the kinetic anesthesia device versus no device
Number of Subjects	50

Main Inclusion and Exclusion Criteria	
 
Key inclusion criteria 
 
Adult volunteers greater than or equal to 18 years of age
 
Able and willing to provide informed consent
 
Able to comprehend and comply with study instructions, and able to complete necessary evaluations.
 
 
 
Key exclusion criteria 
 
Patients unable or unwilling to provide informed consent.
 
Patients with lidocaine allergy
 
Patients with known pain-related or neurological condition.
 
Patients with a known cardiac condition
 
Patients taking medications with a known Clinically Significant Drug Interaction with
 
Vulnerable populations
 
 
 

Investigation al Product (drug, biologic, device, etc.) For Device include the planned use For Drug, food, cosmetic, etc. include the dose, route of administratio n and dose regiment	
 
Blaine Labs Vibration Anesthesia Device. The device will be used as directed by the manufacturer, in the following manner: The device will be held by the person giving the injection in their off hand. It will be firmly pressed on the skin, turned on, adjacent to the injection 1-2 seconds before the injection is given. The injection will be given into the lighted target area of the kinetic anesthesia device. The device will be removed 1-2 seconds after the needle is withdrawn
 
This device is on the US market legally. This is a class 1 device, exempt from the need for approval or clearance. Per the Code of Federal Regulations (https://www.accessdata.fda.gov/scripts/cdrh/cfdocs/cfCFR/CFRsearch.cfm?FR=890.5975-) this device may be used in clinical care or research.
 
The device is being used in this research study in accordance with the FDA description
 

Statistical Methodology	Quantitative VAS data will be analyzed by a two-tailed t-test, and by linear regression model, incorporating location, and order of intervention (i.e. intervention first or second). Quantitative preferential data will be analyzed by logistic regression model incorporating location and order of intervention.
Safety Evaluations	Patients will be monitored for physical discomfort following lidocaine injection by experienced healthcare personnel. Any health-related events will be handled in accordance with standard of care clinical procedures.
Data and Safety Monitoring Plan	The Principal investigator will be responsible for monitoring the data quality and the ongoing safety of subjects.

# BACKGROUND AND STUDY RATIONALE

This study will be conducted in full accordance all applicable University of Pennsylvania Research Policies and Procedures and all applicable Federal and state laws and regulations including [as applicable include the following regulations as they apply 45 CFR 46, 21 CFR Parts 50, 54, 56, 312, 314 and 812 and Good Clinical Practice: Consolidated Guidelines approved by the International Conference on Harmonisation (ICH). Note:Only include ICH compliance if the study will actually comply with these requirements.] All episodes of noncompliance will be documented.

# Introduction

Lidocaine is used widely in the field of dermatology for anesthetizing the skin. It is used commonly for minor procedures such as punch biopsies, and more complex outpatient facial reconstruction after skin cancer removal. Patients consistently experience discomfort from lidocaine injections, particularly since procedures on highly sensitive areas such as the nose and lips are common. Vibrating kinetic anesthesia devices have shown efficacy in reducing the pain of lidocaine injections in dentistry, pediatrics, and dermatology, however no studies exist investigating the effect of these devices on the pain of lidocaine injections on the face.

The proposed study is a split-body randomized controlled trial of kinetic anesthesia devices on pain of lidocaine injection measured by a visual analog scale (VAS). Study participants will be healthy adult volunteers recruited from students, faculty, staff, and others healthy adult within the University of Pennsylvania. The study intervention will be application of the Blaine Labs Vibration Anesthesia Device at the time of injection, according to the manufacturer's instructions. Participants will rate the pain from one injection with the kinetic anesthesia device (KAD) in use, and one injection without the KAD. Ratings will occur on a VAS. Participants will be asked whether they preferred the injection with or without the KAD. Injections will occur at these three sites: lateral forehead, nasofacial sulcus, and lateral back. Participants will be randomized to one of three locations, and to the order of intervention (i.e. first or second injection with KAD). Injections with and without the intervention will occur on the right and left side of the body respectively.

#### 1.1 Background and Relevant Literature

In many dermatologic procedures performed with local anesthetic, the injection of anesthetic is the most painful part of the procedure, and is thus one of the greatest barriers to complete comfort and enhanced patient satisfaction. Methods to minimize injection pain have been proposed and include slow rate of injection, with warmed, buffered lidocaine to decrease discomfort of local anesthetic injection (Kuboa), Vibrating devices have been shown to reduce the pain of local botulinum toxin injections, steroid injections for keloid treatment, local anesthetic injections in eyelid surgery, and in venipuncture in a pediatric emergency department. It is thought that vibration decreases the pain of injection by the gate control theory of pain, first proposed by Melzack and Wall, which asserts that the vibrating neural input overrides painful signals and prevents them from reaching the central nervous system. No study has yet investigated vibration devices for lidocaine injection at multiple body sites in the dermatologic surgery setting. The VAS is reported to be the most frequently used assessment instrument to evaluate the analgesic effects of various therapies and can detect minute pain changes. It has been systematically evaluated by Bijur et al, who determined that a change of 10mm or more on this scale represents a real clinical change in acute pain.

Kuboa et al. Guidelines for the use of local anesthesia in office-based dermatologic surgery. JAAD. 2016;74:6:1201-1219 Sharma P, et al. Investigating the efficacy of vibration anesthesia to reduce pain from cosmetic botulinum toxin injections. Aesthet Surg J.

2011;31:966-971 Park KY, Kim BJ et al. Vibration Anesthesia for Pain Reduction During Intralesional Steroid Injection for Keloid Treatment. Derm Surg. 2017;43:724-727. Fayers, T et al. Vibration-assisted anesthesia in eyelid surgery. Othalmology. 2010;117:1453-1457 Baxter AL et al. An integration of vibration and cold relieves venipuncture pain in a pediatric emergency department. Pediatr Emerg Care.

2011;27:1151-1156 KC Smith, JC Liu et al. Vibration anesthesia: A noninvasive method of reducing discomfort prior to dermatologic procedures. Dermatology Online Journal. 2004;10(2):1 Reed Michael D, van Nostran W. Assessing pain intensity with the visual analog scale: a plea for unity. J Clinic Pharm. 2014; 54:241-244. Bijur PE, Silver W, Gallagher EJ. Reliabil15.

# 1.2 Name and Description of the Investigational Product

Blaine Labs Vibration Anesthesia Device. The device will be used as directed by the manufacturer, in the following manner: The device will be held by the person giving the injection in their non-dominant hand. The vibrating device will be firmly pressed on the skin, turned on, adjacent to the injection 1-2 seconds before the injection is given. The injection will be given into the lighted target area of the KAD. The device will be removed 1-2 seconds after the needle is withdrawn

This device is on the US market legally. This is a class 1 device, exempt from the need for approval or clearance. Per the Code of Federal Regulations (https://www.accessdata.fda.gov/scripts/cdrh/cfdocs/cfCFR/CFRsearch.cfm?FR=890.5975-) this device may be used in clinical care or research.

The device is being used in this research study in accordance with the FDA description

Further information regarding the device is attached in HS-ERA.

# 1.2.1 Clinical Data to Date

Clinical data is summarized in the background section above.

# 2 Study Objectives

### Overall objectives

The purpose of this study is to test the effect of KAD on the pain of lidocaine

injection in healthy adult volunteers at sites with clinical relevance in dermatologic surgery. Primary

Objectives: To determine the effect of KAD versus no device on pain of local anesthetic injection measured by VAS

injection measured by VAS

Secondary Objectives: 1. To determine if the effect of KAD on pain of local anesthetic injection is associated with anatomic location of the injection; 2. To determine subject preference of KAD versus no device for local anesthetic injection; 3. To gather qualitative data on changes to the subjects' experience of pain and overall experience using the KAD versus no device.

# 2.1 Primary Objective

To determine the effect of KAD versus no device on pain of lidocaine injection, participants will be asked to evaluate each injection on a 100mm visual analog scale (VAS). Ratings will be quantified at intervals of 1mm from 1mm to 100mm, with 1 mm representing "no pain at all" and 100 mm representing "worst pain imaginable." VAS ratings from injections with and without the device will be compared in each patient.

# 2.2 Secondary Objectives (if applicable)

To determine if the effect of KAD on pain of local anesthetic injection is associated with anatomic location of the injection, VAS ratings will be used within a statistical model. To determine subject preference of kinetic device versus no device for local anesthetic injection, participants will be asked after the completion of their second injection: "Which method of injection did you prefer overall?" with the following answers: "With the vibrating kinetic anesthesia device being used" "without the vibrating kinetic anesthesia device" and "no preference" To gather qualitative data on changes to the subjects' experience of pain and overall experience using KAD versus no device, patients will be asked the following questions: "Do you have any comments on how the KAD affected your

injection experience?" "Were you bothered in any way by the KAD [check yes or no] if so please comment".

# 3 Investigational Plan

# 3.1 General Design

The study will be an open label split-body crossover trial, using healthy adult volunteers recruited from the faculty, staff and student body of the University of Pennsylvania, and from the University City area of Philadelphia. Participants will be randomized to one of three anatomic sites deemed relevant: the nasofacial sulcus, the lateral forehead, and the upper back. Participants will then be randomized to receive injection with the KAD first or second. The injection will be 0.5 cc of room temperature buffered lidocaine injected at constant slow speed (approximately 5 seconds) through a 30-gauge needle held perpendicular to the skin by the same surgeon, with verbal cues standardized. Injections will be given in accordance with the standard of practice. When the KAD is used it will be used as directed: firmly pressed on the skin adjacent to the injection, with the needle aimed into the lighted area. Volunteers will evaluate each injection immediately after it is complete using the visual analog scale. When both injections are completed, participants will indicate their preference of injection, complete qualitative questions, and note necessary demographic information. Injection location and order of intervention (i.e. first or second) will be noted.

# 3.1.1 Screening Phase

Screening will take place at the time of the study. After informed consent and prior to the start of the investigative procedure, subjects will be verbally asked if they have preexisting cardiac conditions, neurological conditions, or previous adverse reactions to lidocaine.

# 3.1.2 Study Intervention Phase

1. The study will take place in an examination room in the Dermatologic Surgery clinic at the Perelman Center for Advanced Medicine.

2. The KAD used will be the Blaine Labs Vibration Anesthesia Device. The device will be purchased from Blaine Labs directly.

3. Injections will be made up of 0.5mL of room temperature 1% lidocaine buffered with 8.4% sodium bicarbonate, procured from the dermatologic surgery clinic. Injections will use the standard syringe with 30 gauge needle.

4. Before any procedure is done or information is collected for the study, subjects will be asked to read and sign the consent form. Adequate time will be given for subjects to review the Informed Consent Document and review any of their questions or concerns with the study staff or Principal Investigator.

5. Baseline vital signs (heart rate and blood pressure) will be obtained prior to the first injection.

6. Then each subject will be randomized to one location: nasofacial sulcus, lateral forehead or lateral back.

7. Each subject will be randomized to receive the intervention with KAD either first or second.

8. The first injection will always be on the left side and the second will always be on the right

9. When the KAD is used for the injection, it will be held by the person giving the injection in their off hand. It will be firmly pressed on the skin, turned on, adjacent to the injection 1-2 seconds before the injection is given. The injection will be given into the lighted target area of the KAD. The device will be removed 1-2 seconds after the needle is withdrawn.

10. Each injection will be given in accordance with the current standard of practice. Injections will be given using the formulation and needle noted above. Injections will be given with the needle held perpendicular to the skin. The speed of the injection will be slow, aiming for 5 seconds to empty the syringe. All injections will be performed by [name], with verbal cues standardized.

11. After each injection, study participants will be asked to document their level of acute pain using the VAS. A paper and pen version of the scale will be used.

12. After both injections are complete, safety vitals will again be obtained (heart rate, blood pressure) in order to assess whether subject has tolerated the injection without any adverse reactions. If necessary, repeat vitals will be obtained until the Principal Investigator feels the subject is medically clear to leave.

13. After both injections are complete the study participant will be asked to fill out the short questionnaire about preference of injection, qualitative comments, age, and sex.

14. The location and order of the injections will be noted by study personnel. The VAS scales will be measured.

15. At this point, data collection will be complete. Unless an adverse event was noted, or subject has additional questions or concerns regarding their participation or study-related procedures, participants will be compensated and will be free to go at this point.

16. The kinetic anesthesia device will be cleaned with an alcohol swab. Study personnel will wash hands and repeat the exercise on the next participant.

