### 3.2 Study Endpoints

### 3.2.1 Primary Study Endpoints

Each injection will be evaluated by 100mm visual analog scale (VAS) for acute pain immediately after the injection is complete. Patients visually indicate by drawing on paper where their pain is on a 10 cm line, with one end labelled no pain at all and the other worst pain imaginable. The primary endpoint is a statistically significant mean reduction in acute pain on VAS of 10mm or more, per Bijur et al, who determined that this change indicates a real clinical change in acute pain.

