# 8 Statistical Plan

# 8.1 Primary Endpoint

Each injection will be evaluated by 100mm visual analog scale (VAS) for acute pain immediately after the injection is complete. Patients visually indicate by drawing on paper where their pain is on a 10 cm line, with one end labeled no pain at all and the other worst pain imaginable. The primary endpoint is a statistically significant mean reduction in acute pain on VAS of 10mm or more, per Bijur et al, who determined that this change indicates a real clinical change in acute pain. Quantitative VAS data will be analyzed by a two-tailed t-test, and by linear regression model, incorporating location, and order of intervention (i.e. intervention

first or second).

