# 8.3 Sample Size and Power Determination

Sample size was calculated in STATA using the change in VAS needed for clinical significance, in concordance with effect sizes and standard deviations from previous studies. Sample size calculated to detect a clinically significant difference at each of three locations with alpha = 0.05 and a power of 0.8.

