# **10.2 Data Collection and Management**

Paper-based records will be kept in a secure location and only be accessible to personnel involved in the study. Paper based records will be input into a secure electronic database and the paper records will be destroyed as soon as is possible.

Computer-based files will only be made available to personnel involved in the study through the use of access privileges and passwords, and will be kept on password-secured computers.

Wherever feasible, identifiers will be removed from study-related information, with subjects assigned unique non-identifiable study IDs.

Each subject will be assigned a random study ID number, and a key will be used to link this number to their identifiable information. This link will be used only to track adverse events if they occur.

Study data, i.e. visual analog scale ratings, preferences, and demographic information will not be connected with names, birth dates, or MRNs at any time. Data will be collected in this manner on paper and will be immediately encoded in a secure computer database, and the paper records will be kept securely until after the closure of the study with the IRB.

Electronic identifiable information will be stored on the Penn Medicine server and that any paper documents with identifiers (such as consent forms) will be stored in a secure location under lock and key.

Data will be kept on password-protected computers.

A resource at the University of Pennsylvania that can assist you in developing and maintaining data collection and management systems is the Clinical Research Computing Unit (CRCU) in the Center for Clinical Epidemiology and Biostatistics (CCEB) Records Retention

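### The VAS lines are measured in the same visit step that records injection order, and the plan neither names nor masks the reader; coded batch reading would close this small, avoidable route for bias

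*Combined protocol and SAP*

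**What the plan says.** Section 3.1 sets the design: "The study will be an open label split-body crossover trial". The participant makes the rating (3.2.1): "Patients visually indicate by drawing on paper where their pain is on a 10 cm line". Section 3.1.2 adds: "A paper and pen version of the scale will be used". Someone must therefore turn each mark into a number, and section 2.1 gives the resolution: "Ratings will be quantified at intervals of 1mm from 1mm to 100mm".

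That conversion is step 14 of section 3.1.2, repeated word for word in section 6.1: "The location and order of the injections will be noted by study personnel. The VAS scales will be measured". Step 15 then declares data collection complete and lets the participant go, so the reading belongs to the visit. The second sentence of step 14 is passive. It names no reader, and no section asks for a masked or duplicate reading.

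The readings feed the primary endpoint directly (8.1): "The primary endpoint is a statistically significant mean reduction in acute pain on VAS of 10mm or more".

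Section 10.2 bears on any remedy. It already provides a code: "Each subject will be assigned a random study ID number". It also has data entered in the database at once. On the paper records it says two things: in one place they are destroyed at the earliest opportunity, in another they are kept until the study is closed with the IRB.

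**The concern.** In an open-label trial, the steps that can be masked are worth masking. Reading a pen mark against a ruler is one of them. If the reader knows which line belongs to the device injection, a slight lean in the expected direction, repeated across participants, does not average out. It shifts the mean paired difference by its full amount, and a larger sample does not shrink it. The endpoint also has a fixed 10 mm cut-off, so a shift of 1 mm is a tenth of the threshold.

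At stake are the error rate of the t-test and, when the true effect lies just under 10 mm, whether the observed mean reaches the threshold.

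**Working it through.** **Inputs from the documents.** N = 50 (4.6); 1 mm reading steps (2.1); two-tailed t-test and 10 mm threshold (8.1); alpha 0.05 and power 0.8 (8.3). Section 8.1 does not say whether the t-test is paired. Section 2.1 compares the two ratings within each participant, so a paired test is used here.

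**Inputs assumed.** The SD of the paired difference (section 8.3 gives no figure) and the net reading error b, defined as the error on the no-device line minus the error on the device line. If each line is read 0.5 mm in the expected direction, b = 0.5 + 0.5 = 1 mm.

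**Step 1: the plan's own figure.** Section 8.3 states: "Sample size calculated to detect a clinically significant difference at each of three locations with alpha = 0.05 and a power of 0.8". Without an SD, N = 50 cannot be reproduced. Solving backwards, 50/3 gives 16 or 17 participants per location. A paired two-sided t-test with 80% power for 10 mm then implies an SD of the difference of about 13.3 mm (n = 16) to 13.8 mm (n = 17). The value 13.6 mm lies in that interval; 20 and 30 mm cover less favourable cases.

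**Step 2: how reading error enters.** Observed mean difference = true mean difference + b. Non-directional error affects only the spread: 1 mm SD per line moves an SD of 13.4 mm to sqrt(13.4² + 2 × 1²) = 13.47 mm, which is negligible. Only directional error matters.

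**Step 3: rejection rate at no true effect.** The noncentrality is b / (SD/√50), referred to a noncentral t distribution with 49 degrees of freedom and critical value 2.01.

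| SD (mm) | SD/√50 | Noncentrality, b = 1 | Rejection, b = 1 | Rejection, b = 2 |
|---|---|---|---|---|
| 13.6 | 1.923 | 0.520 | 8.0% | 17.5% |
| 20 | 2.828 | 0.354 | 6.4% | 10.7% |
| 30 | 4.243 | 0.236 | 5.6% | 7.5% |

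With b = 0 the rate is 5.0% in every row.

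**Step 4: the 10 mm rule.** Significance needs an observed mean of about 2.01 × SD/√50, which is 3.9, 5.7 and 8.5 mm for the three SDs. All are below 10 mm, so the 10 mm cut-off is the binding condition. By normal approximation, P(observed mean ≥ 10) = 1 − Φ((10 − true − b)/(SD/√50)).

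| SD (mm) | True 0, b = 1 | True 9, b = 0 | True 9, b = 1 |
|---|---|---|---|
| 13.6 | 0.000001 | 0.30 | 0.50 |
| 20 | 0.0007 | 0.36 | 0.50 |
| 30 | 0.017 | 0.41 | 0.50 |

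For example, at SD 13.6 mm with a true reduction of 9 mm and no error, (10 − 9)/1.923 = 0.52 and 1 − Φ(0.52) = 0.30. With b = 1 the numerator is zero and the probability is 0.50.

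**The case against.** The strongest reply is that reading a line in 1 mm steps leaves little room for judgement, and that mark width and rounding do not in themselves create bias. Rounding has no direction. A consistent rule for a wide mark, such as always taking its centre, affects both lines alike and cancels in the paired difference. Bias needs the reader to treat device and no-device marks differently, on average, over the whole sample, and nothing in the documents suggests this. All of that stands. It is why b is an assumption here and not an estimate.

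A reader might infer from step 14 that the person who has just recorded the order also measures the lines. The sequence makes this plausible, but the wording does not establish it, and no reader is named. The data collection sheet is an attachment outside the text reviewed, so the labelling of the VAS forms is unknown too. A reader might also take the 8.0% or 17.5% as the chance of falsely declaring the trial a success. It is not: the endpoint also requires a 10 mm mean reduction, and step 4 shows how rarely that happens with no true effect. Finally, it is tempting to call masked reading free. The documents say nothing about staffing or cost.

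It is also fair to say that the participant, who makes the rating, knows whether the device was used, and that this is the larger open-label bias. That limits what masked reading can achieve. It is not a reason to leave open a route that can be closed.

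**Conclusion.** The point holds as a cheap improvement and does not show a defect that invalidates the trial. The plan has the primary-endpoint lines read during the visit, in the step where order is noted, and leaves the reader unnamed and unmasked. A net directional error of 1 mm would move the t-test's rejection rate at no true effect from 5% to between 5.6% and 8.0% for SDs of 30 down to 13.6 mm. Its practical effect is confined to true reductions near the threshold: at 9 mm, the chance of an observed mean of at least 10 mm rises from 0.30-0.41 to 0.50. The calculation rests on an assumed error, an SD that the documents do not give, and a paired analysis of all 50 participants. The gap in the text does not depend on these assumptions.

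**What to change.** Label each VAS sheet only with the study ID and 'injection 1' or 'injection 2', and keep order and location on a separate sheet. Have existing staff measure all lines in one shuffled batch, with one fixed convention for reading a wide mark, before the order file is merged. State in step 14 of both 3.1.2 and 6.1 who measures, when, and that order is not available to them.

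Section 10.2 must change as well. Exempt the VAS values from immediate entry, and reconcile the two statements on paper records so that the sheets are kept at least until they have been read.

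The cost is a revised form, later entry of the VAS values and secure storage of the sheets in the meantime. Sample size, alpha and the analysis do not change. The fix removes knowledge of order from the reading only; the participant's knowledge of device use remains.
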